Additional outcomes will include: intraoperative minutes from NMBR administration to qTOF T4/T1 >0.9 , to extubation, and total in operating room time; incidence of residual NMB in PACU based on qTOF; number of events and accumulated minutes of hypoventilation in PACU; frequency of patients with ≥ 1 events of delayed postoperative hypoventilation (daily for up to 3 postoperative days) and accumulated minutes of hypoventilation; delayed recurrence of NMB based on qTOF; presence of pre-defined postoperative pulmonary complications during hospital stay and by the postoperative day 14 ± 3 ; standardized Patient-Reported Outcomes Measurement Information System (PROMIS®) dyspnea functional limitations questionnaire score compared to patient's baseline; pre-defined kidney graft outcomes; hospital resources utilization (e.g. hospital length of stay, ICU admission) and their cost estimates.

[figure not shown]
B. Description of Population to be Enrolled

We will include adults (≥ 18 years and ≤ 90) diagnosed with severe kidney dysfunction (defined by plasma creatinine clearance <30 mL/min) and planning on kidney transplantation surgery at the University of Colorado Hospital. Exclusion criteria: patients unable to sign the informed consent, pregnant women, Body Mass Index (BMI) > 40 , pre-existing oxygen or ventilatory dependency (24h use of oxygen or other noninvasive or invasive ventilatory support), or patients with any pulmonary, neuromuscular or other disease that severely limits their respiratory functional status (e.g. unable to achieve 4 Metabolic Equivalent of Tasks, METs, such as climbing up 1 flight of stairs[32]), or any contraindication for any of the study-related medications or interventions.

C. Study Design and Research Methods

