We have designed a prospective randomized double-blind single center study on 100 patients with severe kidney failure undergoing kidney transplantation surgery. Patients will be randomized to receive either NMB with rocuronium and sugammadex for NMBR (intervention group) or NMB with rocuronium and neostigmine for NMBR (control group). Respiratory function will be objectively monitored starting in PACU and during the first 3 postoperative days or until end of monitoring criteria are met. A blinded assessor will record the frequency of hypoventilation events as well as the accumulated minutes of hypoventilation. Quantitative TOF monitoring will be evaluated by a blinded investigator. Additional data related to patient's comorbidities, morphine equivalents (mg/kg) received, validated dyspnea patient-reported scores, pulmonary complications, kidney graft relevant data and outcomes, and hospital resource utilization and estimated costs will also be collected.

After signing informed consent, patients will be randomized to receive, during kidney transplant surgery, NMB with rocuronium and NMBR with either sugammadex (intervention group) or neostigmine (control group). Both groups will receive intraoperative NMB agents and reversal medications as guided by qTOF monitoring and following FDA-approved doses (see details below). In the PACU, we will perform continuous monitoring of their MV during their PACU stay and assess qTOF at selected time points in all patients. Institutional discharge criteria from PACU is based on an Aldrete's score[33] ≥ 8 assuming there are no discharge concerns by the patient's healthcare providers (PACU nurse, anesthesiologist and/or surgeon). After discharge from PACU and during the first 3 postoperative days (or until end of monitoring criteria if sooner) we will maintain the continuous MV monitoring and daily quantitative TOF assessment, collect opioids received and data relevant to pulmonary complications, kidney graft outcomes and estimated healthcare costs. At the postoperative surgery clinic visit or by phone interview we will collect patient's subjective dyspnea scores and compare to their baseline (with a validated questionnaire), as well as updated PPCs, kidney graft outcomes, hospital resources utilization and estimated healthcare costs.

Preoperative phase

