Screening for eligibility and consenting will take place once the patient has been accepted for kidney transplantation at the University of Colorado Hospital by the Transplant Surgery team. Randomization will occur after patients consent for the study. Only the PI will remain unblinded to the group allocation (see below).

Preoperative data will be collected by the blinded investigator (study coordinator), including baseline vital signs (including room air SpO₂), comorbidities, medications, and kidney graft relevant factors. The baseline dyspnea scores will be assessed by asking patients to complete the PROMIS® v1.0 Dyspnea Functional Limitations Short Form 10a_9-2-2016 questionnaire (available at http://www.healthmeasures.net/administrator/components/com_instruments/uploads/PROMIS%20SF%20v1.0-Dyspnea%20Functional%20Limitations%2010a_9-2-2016.pdf). This is a validated and standardized short questionnaire to quantitate if sugammadex used for NMBR reduces the subjective dyspnea scores relative to baseline.

Intraoperative phase

We will perform a prospective parallel randomized study of rocuronium/sugammadex (intervention) vs. rocuronium/neostigmine (control) for NMB and NMBR at the end of kidney transplantation surgery. This will be performed by the unblinded investigator, following the following protocol(s):

- A quantitative TOF (qTOF) monitor (the Stimpod NMS450®, Xavant Technology Ltd., South Africa, the acceleromyography-based monitor available at UCH, and/or the TwitchView™, Blink Device Company, Seattle, WA, an electromyography-based monitor) will guide the NMB and NMBR management in all study patients. Quantitative NMB monitoring are considered superior to the more routinely-used but subjective qualitative TOF monitors[34, 35]. The qTOF monitor will be placed in the ulnar nerve territory to stimulate the adductor pollicis muscle[36] immediately after loss of consciousness during induction of anesthesia. The exact location of monitoring will be marked and used for qTOF measurements in the postoperative period.
- NMB brief protocol: Rocuronium will be the NMB agent used in both groups as guided by the qTOF and following standard dosing protocols in order to achieve adequate NMB to allow the intubation and surgical procedure (routinely T4/T1 < T3 until closure of surgical incision). Rocuronium dosing: 0.6-1.2 mg/kg for intubation, 0.08-0.2 mg/kg bolus for maintenance with recovery of second twitch (T2) in qTOF.

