- The blinded investigator will assess the presence of residual NMB with the quantitative TOF monitor by calculating the average of 3 measurements of qTOF $T4/T1$ (40mA or adequate to achieve TOF response while comfortable for the patient) within 15min of PACU arrival and hourly until up to 3h after the end of surgery or sooner if the patient meets PACU discharge criteria. We will record the initial PACU TOF and calculate the PACU average TOF. After transfer to the postoperative floor, the blinded investigator will assess residual or recurrent NMB with the qTOF monitor twice a day, with 3 repetitions each time, and each assessment separated by ≥ 6 h. This will be maintained for up to 3 days after the end of surgery or until end of monitoring criteria are met.
- The individual doses of administered opioids received by the patient during the study (PACU and daily for up to 3 postoperative days or until the end of monitoring criteria are met) will be recorded and converted to morphine equivalents[21] to statistically evaluate the effect of opioid administration on hypoventilation events.
- Nursingcharted episodes of respiratory depression during the PACU stay will also be recorded. Postoperative pulmonary complications (as defined elsewhere[13]) during PACU and up to 3 postoperative days will be collected.

Postoperative end of study follow-up

At postoperative day 14 ± 3 during the patient's visit to the transplant surgery clinic or via a phone call, the PROMIS® Dyspnea Functional Limitations Short Form questionnaire will be repeated

and normalized to the patient's baseline. Any postoperative pulmonary complications[13] and hospital resources utilization occurring from the hospital discharge until this end of study follow-up will be collected from the patient and the medical record, and the estimated costs based on average hospital daily stay depending on type of care unit or reported cost of complications calculated.

Any signs and symptoms of hypersensitivity (e.g. rash, anaphylaxis) detected during PACU and up to 3 postoperative days will be collected from the patient and patient's providers. The relationship of these signs and symptoms to sugammadex will be assessed by the patient's providers and also by the study safety officer. Their confirmatory diagnostic testing and management will be performed at the discretion of the patient's providers.

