Incidence of residual or recurrent NMB in the postoperative floor. This will be calculated as described before (T4/T1 <0.9 , considered severe if T4/T1 <0.4), as an average of 3 repetitions obtained on two occasions separated by ≥ 6 h daily on postoperative days 1-3 or until the end of monitoring criteria have been met.

Morphine equivalents will be calculated from individual opioid doses administered to each patient following standard conversion formulas[21, 40]. This morphine equivalent dose will be calculated for the PACU period and daily for 3 first postoperative days or until the end of monitoring criteria have been met, and used as covariate in the logistic regression analysis.

Time from NMBR administration to quantitative TOF T4/T1 >0.9 (minutes, one decimal). The quantitative TOF will be repeated at 80 mA every 30 seconds from the moment the NMBR medication (sugammadex or neostigmine) has been completely administered intravenously.

Time from NMBR administration to extubation (minutes, once decimal).

Time of total operating room time (minutes), counting from in-room time stamp to out-of-room time stamp.

The PROMIS® v1.0 Dyspnea Functional Limitations Short Form 10a_9-2-2016 questionnaire is a validated and standardized short questionnaire to quantitate if sugammadex used for NMBR reduces the subjective dyspnea scores relative to baseline. It will be completed by the patient in the preoperative phase and during the postoperative follow up. It is available at http://www.healthmeasures.net/administrator/components/com_instruments/uploads/PROMIS%20SF%20v1.0-Dyspnea%20Functional%20Limitations%2010a_9-2-2016.pdf.

Postoperative Pulmonary Complications (PPCs) following previous definitions[13, 41, 42], including:

Respiratory Failure, defined as[41]: "When postoperative $\text{PaO}_2 < 60\text{mmHg}$ on room air, a ratio of PaO_2 to inspired oxygen fraction < 300 or arterial oxyhemoglobin saturation measured with pulse oximetry (SpO_2) $< 90\%$ and requiring oxygen therapy".

Unplanned intubation with postoperative mechanical ventilation (POMV), defined as placement of a breathing tube that was not intended or planned, excluding instances of intubation during an unplanned return to the operating room. Also excluded those patients that were transferred intubated and ventilated to the intensive care unit (ICU) from the operating room.

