The secondary analysis comparing delayed efficacy of sugammadex to neostigmine in reducing the incidence of hypoventilation during the first 3 postoperative days will assume the same model and covariates as the primary hypothesis. To compare the incidence of PPCs a logistic regression model will be used with the binary outcome of any PPC and will include covariates for group and total morphine equivalents. Hospital length of stay and costs will be compared between groups using a linear regression model including covariates for group, total morphine equivalents, presence of respiratory comorbidities and other clinical differences that may influence the outcome. Continuous outcomes may be transformed if they violate the normality assumption (e.g., a log-transformation).

Multiplicity

Given only one primary outcome and hypothesis, there is a not a concern for multiplicity. Secondary analyses are considered exploratory in this protocol.

Power/Sample Size:

Based upon a sample size of 40 patients per group, this study has 90% power to detect a 50% difference in hypoventilation incidence in the PACU (from 76% as reported in previous studies[21] to 38%, alpha 0.05), assuming a potential dropout of up to 6 patients per group. The 50% reduction is considered clinically relevant for a decrease in the frequency of hypoventilation, a precursor of more clinically significant complications such as hypoxemia, reintubation or pneumonia. Quantifying the contribution of hypoventilation into more severe complications is challenging, and details of duration and severity of hypoventilation are not well known. Thus, only a significant reduction in hypoventilation incidence (i.e. 50%) may be accepted as relevant. This trial will provide additional detailed information that may provide more insight on the clinical consequences of hypoventilation (e.g. potential association between accumulated minutes of MV <40% expMV and decrease in SpO₂/FiO₂ over the following 30 min).

A sample size of 40 patients per group would also have approximately 80% power (78%) to detect a difference in case the incidence of any hypoventilation events is 60%, instead of the literature-based 76%. The table below provides the sample size per group to achieve a variety of assumptions for the primary outcome, alpha, and power:

Incidence Group 1	Incidence Group 2	Alpha	Power	Sample Size per Group
1. 0.76	2. 0.38	3. 0.01	4. 0.8	5. 39
6. 0.76	7. 0.38	8. 0.05	9. 0.8	10. 26

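### The day-14 PROMIS dyspnea score is to be normalised to baseline by an undefined operation, with no model and no baseline covariate; unadjusted, the comparison loses precision

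*Combined protocol and SAP*

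**What the plan says.** Lower reported dyspnea is the first of the additional secondary objectives. Section III.C, Preoperative phase, provides the baseline: "The baseline dyspnea scores will be assessed by asking patients to complete the PROMIS" form before surgery. The form is repeated at day 14 ± 3.

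Each description of how the repeat score will be used sets it against the patient's own baseline:

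- III.C, Postoperative end of study follow-up: the repeat questionnaire is taken "and normalized to the patient's baseline".
- III.A, Outcome Measure(s): "dyspnea functional limitations questionnaire score compared to patient's baseline".
- III.C, Study Design and Research Methods: "collect patient's subjective dyspnea scores and compare to their baseline".
- III.C, Preoperative phase, and III.F, Variables/Time Points of Interest: the form is there to show whether sugammadex "reduces the subjective dyspnea scores relative to baseline".

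III.F, Statistical Methods, gives models for hypoventilation, pulmonary complications, length of stay and costs. The only continuous outcomes with a model are the last two: "Hospital length of stay and costs will be compared between groups using a linear regression model". A general remark adds "Continuous outcomes may be transformed if they violate the normality assumption", which does not deal with baseline. PROMIS is not mentioned there. Under Multiplicity, "Secondary analyses are considered exploratory in this protocol".

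**The concern.** Two things are open: what normalising means (difference, ratio or percent change), and whether the baseline score enters the comparison between groups as a covariate. A reader who follows the text as it stands would compute a score relative to baseline and compare it between arms, with no further adjustment.

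That uses the baseline inefficiently. Subtracting it in full fixes its slope at 1. When the true slope is lower, the change score stays negatively correlated with baseline, so a chance difference between the arms before surgery carries into the result. Regression on baseline estimates the slope and removes this. At stake are the precision of a named secondary comparison in a small trial, and the freedom to choose among several analyses once the data are in hand.

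**Working it through.** **Inputs.** From the documents: baseline and day-14 scores are collected, 40 patients per group are planned, and up to 6 per group may drop out, leaving 34 (III.F, Power/Sample Size). III.C gives a total of 100 patients; the variance ratios below do not depend on the number. The documents give no PROMIS SD, correlation, effect size or power, so there is no PROMIS figure to reproduce. Assumed: equal SD at both visits, and r = 0.3, 0.5, 0.7 or 0.9.

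**Step 1: variance.** In units of SD²:

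- unadjusted change score: 2(1−r)
- follow-up score adjusted for baseline (ANCOVA): 1−r²
- ratio, ANCOVA to change: (1−r²)/(2(1−r)) = (1+r)/2

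| r | Change | ANCOVA | Ratio | Variance lower by | Equivalent extra patients (1/ratio − 1) |
|---|---|---|---|---|---|
| 0.3 | 1.40 | 0.91 | 0.65 | 35% | 54% |
| 0.5 | 1.00 | 0.75 | 0.75 | 25% | 33% |
| 0.7 | 0.60 | 0.51 | 0.85 | 15% | 18% |
| 0.9 | 0.20 | 0.19 | 0.95 | 5% | 5% |

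**Step 2: unequal SDs.** Let the follow-up SD be k times the baseline SD. In units of the baseline variance, the change score has 1 + k² − 2rk and ANCOVA has k²(1−r²). The difference is (1−rk)². It is never negative, and it is zero when the slope rk equals 1. So the direction holds in general, apart from the small cost of estimating the slope, but the size depends on k as well as r.

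**Step 3: power, for illustration.** For an assumed true difference of 0.5 SD, two-sided alpha 0.05:

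| r | 40 per group: change vs ANCOVA | 34 per group: change vs ANCOVA |
|---|---|---|
| 0.3 | 47% vs 65% | 41% vs 58% |
| 0.5 | 61% vs 73% | 54% vs 66% |
| 0.7 | 82% vs 88% | 76% vs 82% |
| 0.9 | 99.9% vs 99.9% | 99.6% vs 99.7% |

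**Step 4: check by simulation.** 3000 runs, 40 per group, assumed mean 50, SD 10, difference 5:

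| r | Ratio, unadjusted | Change, unadjusted | ANCOVA | Change plus baseline |
|---|---|---|---|---|
| 0.3 | 44.1% | 47.0% | 63.9% | 63.9% |
| 0.5 | 56.0% | 58.7% | 70.5% | 70.5% |
| 0.7 | 80.1% | 80.5% | 86.5% | 86.5% |

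Change with baseline as a covariate matches ANCOVA exactly. What costs precision is leaving baseline out of the model, not forming a change score.

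**Step 5: chance imbalance.** The standard error of the baseline difference is SD × √(2/40) = 0.22 SD. An imbalance at least that large, in either direction, occurs in about 32% of trials. It shifts an unadjusted change comparison by (1−r) × 0.22 SD: about 0.16, 0.11, 0.07 or 0.02 SD at r = 0.3, 0.5, 0.7 or 0.9. Averaged over randomisations the shift is zero.

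**The case against.** The strongest reply is that the plan never states an unadjusted PROMIS analysis. The word normalised stands in a data-collection section, and phrases such as compared with or relative to baseline do not exclude a covariate. The models that are stated are all covariate-adjusted regressions. This stands as far as it goes: a reader might infer that the sponsor chose a change score in preference to covariate adjustment, and the documents do not show that choice. They show an undefined operation and no model. Followed literally, though, they lead to an unadjusted relative score, and nothing in them points to the more precise analysis.

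Three other readings go too far:

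- **Bias.** A reader might infer that the result would be systematically wrong. Baseline precedes treatment in a randomised trial, so an unadjusted change score is unbiased over randomisations. The issue is precision and the imbalance in the one trial that is run.
- **Unstable ratio.** A reader might infer that dividing by low baseline scores would make the outcome erratic. The documents give neither a scoring range nor an expected mean, so this cannot be assessed. In the simulation above, a ratio was only slightly worse than a difference.
- **A fixed loss.** The percentages apply to an unadjusted difference with equal SDs. SDs may well differ between the days before and after a transplant, and at r = 0.9 little is lost.

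Finally, the outcome is secondary and exploratory, and the Clinical Hypotheses section says that powering such outcomes would need a much larger study. That limits the importance of the point. It does not argue for discarding precision from data already collected.

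**Conclusion.** The point holds as a modest one. The PROMIS endpoint is not fully defined, it has no stated model, and the baseline score is not named as a covariate anywhere. If the score relative to baseline is compared without that covariate, ANCOVA would have 35% to 5% lower variance for r from 0.3 to 0.9. This rests on assumed correlations, equal SDs and an unadjusted difference. The direction of the gain is more secure than its size: it disappears only as the slope on baseline approaches 1. The primary analysis, its power and the sample size are untouched. The change is worth making because it is nearly free and also settles the analysis before the data are seen.

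**What to change.** Add one sentence to III.F, Statistical Methods, for example: *The day-14 PROMIS dyspnea score will be compared between groups by linear regression with group and baseline PROMIS score as covariates.* Using the change score as the response with the same covariates is equally acceptable, because the group effect is identical.

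In III.C, Postoperative end of study follow-up, replace the reference to normalising with wording that matches, such as *analysed with adjustment for the preoperative score*. Have the mentions of baseline in III.A, the other parts of III.C, and Variables/Time Points of Interest read the same way.

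Cost: one added sentence and small wording edits in a protocol amendment. No new data, visits or patients.

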- NMBR brief protocol: The sugammadex (intervention) or neostigmine (control) will be administered at the end of the surgery. The goal will be to administer the appropriate NMBR medication when ≥ 2 twitches are objectivized with the qTOF monitor. NMBR drugs and dosing for each group will follow standard of care FDA-approved doses, as follows: Sugammadex 2 mg/kg will be administered when spontaneous recovery has reached the reappearance of the second twitch in response to TOF stimulation.

	Sugammadex dosing (mg/kg)	Neostigmine dosing (mg/kg)
T4 recovered	2	0.03-0.05 (max 5 mg)
T2/T3 recovered	2	0.05-0.07 (max 5 mg)
T0/T4 with 1-2 post-tetanic twitches present or T1 recovered	4 or wait	Wait

Overdosing of neostigmine will be avoided to prevent neostigmine-induced muscle weakness. Neostigmine will be administered simultaneously with the appropriate glycopyrrolate dose (0.2 mg per 1.0 mg of neostigmine).

Extubation will be performed following the usual standard of care criteria of adequate level of consciousness, presence of airway protection reflexes and spontaneous ventilation parameters in addition to quantitative TOF $T4/T1 >0.9$. The following times (minutes) will be recorded: NMBR administration-to-T4/T1 >0.9 , NMBR administration-to-extubation, total operating room time.

Postoperative in-hospital phase

The blinded investigator will collect the following study-related information:

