Kidney graft outcomes, including postoperative ClCr, daily urine output, need for dialysis postoperatively, diagnosis of delayed graft function, kidney graft rejection. Postoperative hemodialysis is not usually planned and typically reserved for patients with immediate donor graft failure who exhibit signs of congestive heart failure within the first week after transplantation. The need of rescue hemodialysis within the first week after kidney transplantation is an accepted and simple definition of delayed kidney graft function[46].

Hospital resources utilization: hospital floor length of stay (LOS) (days, rounded to half a day), ICU admission and LOS, estimated cost based on average daily cost at a postoperative UCH floor or ICU and/or based on reported estimated costs per PPC[47, 48]

Hypersensitivity adverse events: hypersensitivity signs and symptoms, including but not limited to rash, bronchospasm or anaphylaxis, will be obtained for up to 3 postoperative days directly from the patient and the patient's providers. Their relationship to sugammadex will be assessed by the patient's physicians and the study safety officer. Their confirmatory testing and management will be performed strictly at the discretion of the patient's physicians.

Statistical Methods

The primary hypothesis is that the frequency of patients with one or more episodes of hypoventilation events in PACU (% of patients) is lower in the sugammadex group compared to neostigmine (controls). This will be analyzed by logistic regression which includes as covariates group allocation, total morphine equivalents, and TOF T4/T1 response, and other observed significant and clinically relevant differences between the groups. The odds ratio for the group covariate will be the primary outcome of interest, with the other covariates included in the model to adjust for potential confounders related to hypoventilation.

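### The procedures text opens hypersensitivity collection at PACU, after the reversal drug has been given in the operating room, and no section sets a window that begins at dosing

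*Combined protocol and SAP*

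**What the plan says.** **Dosing.** The NMBR brief protocol in section III.C (Intraoperative phase) states: "The sugammadex (intervention) or neostigmine (control) will be administered at the end of the surgery". Section III.A lists among the additional outcomes "intraoperative minutes from NMBR administration to qTOF T4/T1" above 0.9 and the time to extubation, so dosing, recovery and extubation all belong to the operating-room phase.

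**Hypersensitivity, procedures text.** Section III.C, Postoperative end of study follow-up: "Any signs and symptoms of hypersensitivity (e.g. rash, anaphylaxis) detected during PACU and up to 3 postoperative days will be collected". The sources named are the patient and the patient's providers.

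**Hypersensitivity, variable definition.** Section III.F, Variables/Time Points of Interest, says that these signs and symptoms "will be obtained for up to 3 postoperative days directly from the patient" and from the providers. It gives bronchospasm as an example as well as rash and anaphylaxis. It sets an end and no start.

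**Recording in the operating room.** After dosing, the Intraoperative phase lists times for recording: from reversal to the TOF threshold, then "NMBR administration-to-extubation, total operating room time". Section III.F adds repeated TOF readings. Of the intraoperative protocol as a whole, section III.C says: "This will be performed by the unblinded investigator".

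**The concern.** A collection window for reactions to a drug would normally open when the drug is given. Here the only start that the plan states is arrival in a later care area. Between injection and that arrival the patient recovers to the TOF threshold, is extubated and leaves the room. A transient rash or a short bronchospasm in that interval falls outside the procedures text as written.

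What is at stake is the completeness of a safety item. Section II (Background) says that information on sugammadex in kidney dysfunction is insufficient, so readers will look at the hypersensitivity count. If it omits the interval in which exposure starts, a low or zero count means less than it appears to.

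**Working it through.** There is no figure in the plan to reproduce. The check is to put the plan's own timeline beside its collection rules.

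1. **Sequence of events** (sections III.A and III.C): reversal drug given; TOF ratio above 0.9; extubation; out of the operating room; PACU arrival; floor, for up to three postoperative days.
2. **Procedures text:** opens at PACU and closes at three postoperative days. The interval from injection to PACU arrival is not included.
3. **Variable definition:** closes at three postoperative days, with no opening point. It neither includes nor excludes the operating room, so it does not settle the matter.
4. **Operating-room records:** times and TOF readings only. No safety item is listed, and no one is assigned to record one. The study coordinator's tasks in section III.F are the preoperative and postoperative assessments.
5. **Pulmonary complications as a second route:** bronchospasm is defined in section III.F and taken from the medical chart. Section III.A counts postoperative pulmonary complications over the hospital stay, but section III.C (Postoperative in-hospital phase) words their in-hospital collection from PACU. Whether this route reaches an operating-room bronchospasm is unclear.
6. **General safety wording:** adverse-event communications appear in section III.F in connection with a low postoperative TOF, and the opening of that section mentions an independent safety review. Neither sets a collection window.

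The result, by when the reaction occurs:

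- It begins at dosing and is still visible in PACU: captured.
- It begins and resolves before PACU arrival: not captured under the procedures text.
- It keeps the patient from reaching PACU: the stated opening point never occurs, so coverage is undefined at best.
- It begins in PACU or later, up to day 3: captured.

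**How much one event matters.** This is an illustration only, because the documents give no event rate. Assume equal allocation of the 100 patients in section III.C, so 100 / 2 = 50 per arm. With no events, the upper limit of the exact two-sided 95% interval is 1 − 0.025^(1/n). With one event, it is the p that solves (1 − p)^n + n·p·(1 − p)^(n − 1) = 0.025.

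- n = 50: 7.1% with no events, 10.6% with one.
- n = 40 (the group size in Power/Sample Size): 8.8% with no events, 13.2% with one.

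At this size, one unrecorded event visibly changes what the count can rule out.

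**The case against.** The strongest reply has three parts.

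**The variable definition is open at the start.** It can be read as covering the operating room. That is so, but it does not say it, while the procedures text names PACU. At best the two sections differ in scope and need to be aligned.

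**Events in the operating room are not unobserved.** The unblinded investigator runs the intraoperative protocol, the providers who are a named source include the anesthesiologist, and there is an independent safety review. This stands. The documents do not show that an anaphylaxis at injection would be lost to all reporting. It does not repair the planned safety item, because none of these provisions states a window from dosing, and a mild sign that passes quickly may not be raised by any of them.

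**The consequence is limited.** Reactions still present in PACU are captured. This also stands.

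A reader might go further and infer two things that the documents do not support. The first is that hypersensitivity is the trial's only named drug-safety outcome. It is not: section III.F also defines residual or recurrent blockade, with a severe category and immediate reporting, and bronchospasm as a pulmonary complication. The second is that a between-arm safety comparison is biased. No such comparison is planned. Hypersensitivity is absent from the outcome list in section III.A and from Statistical Methods, and what is described is a case-by-case assessment of relationship to sugammadex by the providers and the safety officer.

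**Conclusion.** The point holds in a limited form. The procedures text puts the start of hypersensitivity collection after exposure, the variable definition does not correct this, and no other section sets a window from dosing. The consequence is possible under-recording of a descriptive safety item, confined to reactions that resolve before PACU arrival or prevent it.

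The size of the under-recording is unknown: the plan gives neither a reaction rate nor the share expected to resolve in that interval. The conclusion rests on reading the procedures text literally and on the order of events in sections III.A and III.C. It does not touch the primary outcome, its analysis or the sample size.

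**What to change.** State the same window in both places (section III.C, Postoperative end of study follow-up, and section III.F, Hypersensitivity adverse events): from administration of the reversal drug, in both arms, through postoperative day 3. Name the anaesthesia record as a source for the interval between dosing and PACU arrival.

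Say who reads that record. Section III.F requires the coordinator who makes the postoperative assessments to stay blinded, and the record presumably shows which reversal drug was given (an assumption; the documents do not say). The extraction should therefore fall to the investigator who is already unblinded, or to the safety review monitor who has the group codes.

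The cost is a short amendment to two paragraphs and a review of one existing record per patient. There is a small downside: operating-room events would be recorded by someone who knows the allocation. Applying the same list of signs to every patient in both arms would limit this. The change concerns data collection only and leaves clinical management as it is.
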